7 ADVERSE EVENTS: LIST AND REPORTING REQUIREMENTS

Adverse event (AE) monitoring and reporting is a routine part of every clinical trial. The following list of AEs (Section 7.1) and the characteristics of an observed AE (Sections [7.2](#) and [7.3](#)) will determine whether the event requires expedited reporting via the CTEP Adverse Event Reporting System (CTEP-AERS) **in addition** to routine reporting".

- Baseline Abnormalities

Any baseline (pretreatment) abnormalities observed during the initial physical examination should be recorded in the Rave database.

- Treatment or within 30 days of treatment

Only record Grades 1 and 2 adverse events if the attribution is at least possibly related to PD-0332991. Record all adverse events Grades 3 through 4 and deaths), regardless of attribution on the electronic case report forms.

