2.4.2 Rationale for Pharmacokinetic Studies

Because the pharmacokinetics of this agent are relatively unknown in the pediatric population, this information will be essential for evaluating toxicity and disease response and for refining dosing in future clinical trials of PD-0332991. The results of these studies will provide the basis for assessing the relationship between the disposition of PD-0332991 in adult and children. Mandatory pharmacokinetic studies are needed to characterize the disposition of PD-0332991 in this patient population. Insights into the biologically active dosage will be gained by relating PD-0332991 systemic exposure (e.g., AUC) to results of pharmacodynamic studies (e.g., percentage change in ANC and platelets compared to baseline).

In vitro studies indicate that PD-0332991 is a substrate of CYP3A4, and dexamethasone is a known inducer of CYP3A4. Thus, one might expect lower exposures of PD-0332991 when administered concurrently with dexamethasone. Indeed, following multiples doses of PD-0332991 in A5481004 Phase 2 (dosing Schedule B), the mean PD-0332991 24-hr trough drug concentrations seem to decrease with time. The mean PD-0332991 trough concentrations on Cycle 1 Day 8, Cycle 1 Day 11, and Cycle 2 Day 11 were 45.33, 44.09, and 32.00 ng/mL, respectively, which is suggestive of a decreased PD-0332991 exposure when administered after dexamethasone-mediated enzyme induction has occurred. It should be noted that the exposure of PD-0332991 observed in this study is considerably lower compared to those observed in Studies A5481001 and A5481003 at the dose levels likely due to the induction effect of dexamethasone. Hence, patients who are receiving dexamethasone will have optional plasma PK studies done following discontinuation of this drug.

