5.5.1 On Study Data Submission Schedule

Pre-treatment, on-study and off-treatment data, as well as patient response data are to be recorded in the electronic data collection screens using the Rave database. See the Required Data and Timetable for Submission form located on the PBTC-042 Protocol webpage for the schedule. For assistance, contact the PBTC Protocol Coordinator listed on the cover page. An optional roadmap is located on the PBTC-042 Protocol Webpage.

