10 STUDY CALENDAR

	Pre-therapy	Course 1	Course 2- Course 26	Completion/ Discontinuation Of Treatment
PHYSICAL ASSESSMENTS				
Medical history	X	Weekly	X	X
Physical exam /height/weight	X	Weekly	X	X
Vital signs	X	Weekly	X	X
Performance status	X	Weekly	X	X
Neurologic exam	X	Weekly	X	X
LABORATORY EVALUATIONS				
CBC - WBC, HgB, Hct, Platelets, ANC, ALC	X	Weekly ^A	Weekly ^{A, B}	X
Serum Chemistry - Sodium, Potassium, Bicarbonate, Chloride, Calcium, BUN, Creatinine, Glucose, Phosphorous, Magnesium, Albumin, Total Protein	X	Weekly	X ^B	X
SGPT (ALT), SGOT (AST), Alkaline phosphatase, Total Bilirubin	X	Weekly	X ^B	X
Serum pregnancy test (for females of childbearing potential)	X	X ^B	X ^B	
CSF cytology (if clinically indicated)	X			
OTHER ASSESSMENT				
12-lead EKG	X	X ^C	X ^C	X ^C
Ophthalmology Examination (including slit lamp)	X		X ^D	
IMAGING ASSESSMENTS				
Brain MRI (standard)	X		X ^E	X
Spine MRI (if clinically indicated)	X		X ^F	X
CORRELATIVE STUDIES				
Screening Pre-trial tumor materials for Rb1 testing (required for patients with all types of CNS tumors except DIPG, medulloblastoma, ATRT)	X ^G			
Pharmacogenetic Studies (if consented)	X ^H			
Plasma Pharmacokinetic Studies (required)	X ^I	X ^I		
Plasma PK after discontinuation of dexamethasone (if consented)		Any time after stopping dexamethasone ^I		
Pre-trial tumor materials for Genomics (if consented)	X ^J			
Tumor Tissue and blood for Biorepository (if consented)	X ^K			

	Pre-therapy	Course 1	Course 2- Course 26	Completion/ Discontinuation Of Treatment

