
A. CBC with differential at baseline and q weekly during each cycle for the first 3 cycles; consideration can be given to increase interval to q 2 weeks from course 4 onwards if the patient has no DLT in the previous cycle. If patient develops Grade 4 neutropenia or thrombocytopenia, then CBCs should be checked every 3-4 days until recovery to Grade 3.
 
B. Within 48 hours of beginning protocol therapy and each course (see 5.3).
 
C. 12-lead EKG at baseline, and 3 hours post dose on days 1, 8, and 15 of cycle 1 and on day 1 of cycles 2 and 3. Thereafter, EKG should be done prior to the start of every 3rd cycle (prior to 6, 9, 12, 15, 18, 21, 24 and end of treatment).
 
D. Eye exam is to be done at baseline, and every 3 months (after courses 3, 6, 9, 12, 15, 18, 21, 24). The ophthalmology exam report should clearly specify the presence or absence of cataracts and data must be recorded in Rave database.
 
E. Standard imaging is to be done every 8 weeks (after courses 2, 4, 6) and then every 12 weeks thereafter through the 26 courses and at the completion of treatment.
 
F. MRI Spine should be done at the same time points as the standard MRI brain, if clinically indicated.
 
G. 2 unstained slides from FFPE block and 1 H&E slide required to be submitted for Rb testing (see 9.1.1)
 
H. Obtain 5 mL of whole blood prior to 1st dose if consented (See section 9.2.1 for details)
 
I. Plasma PK (required) – D1 Course 1: pre-dose, 0.5, 1, 2, 4, 8, 10, 24, 48 hrs after dose D21 Course 1: pre-dose, 1, 2, 4, 8, 10, 24 after dose (See section 9.2.2 for details of Plasma PK) Plasma PK after discontinuation of dexamethasone (if consented) – see section 9.2.2
 
J. 10 unstained slides from FFPE block or FFPE tissue block [See section 9.3.3 for details of Pre-trial tumor materials for Genomics (if consented)]
 
K. Biorepository samples (if consented) – 20 unstained FFPE slides and blood. Obtain 2-5 mL of whole blood at baseline. If unable to collect at baseline, it can be collected any time during protocol therapy. See section 9.3.1 for details.
				

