12.3 Participant and Data Confidentiality

Participant confidentiality is strictly held in trust by the participating investigators, their staff and the sponsor(s) and their agents. This confidentiality is extended to cover testing of biological samples and genetic tests in addition to the clinical information relating to participants. Therefore, the study protocol, documentation, data and all other information generated will be held in strict confidence. No information concerning the study and the data will be released to an unauthorized third party without the prior written approval of the Pediatric Brain Tumor Consortium (PBTC).

The PBTC protocol coordinators, other authorized representatives of the sponsor, regulatory representatives, PBTC auditors, representatives of the IRB or the pharmaceutical collaborator supplying study product may inspect all documents and records required to be maintained by the investigator, including but not limited to, medical records (office, clinic, or hospital) and pharmacy records for the participants in this study. The clinical study site will permit access to such records.

Source documents which are the original records of clinical findings, observations or activities in a clinical trial are to be maintained at each participating site. Sites must upload all source documentation which supports the eligibility of the participant to the PBTC via the RAVE database. In the event the patient experiences unexpected events, additional source documentation may be requested to complete the event review. These documents may include but are not limited to, hospital records, clinical and office charts, laboratory notes, memoranda and radiographic images.

Study participant study related data, which is for purposes of statistical analysis and scientific reporting will be transmitted to the Pediatric Brain Tumor Consortium electronically via the RAVE database. This will not include the participant's contact or identifying information. Rather, research participants and their research data will be identified by a unique study identification number assigned at the time of screening or registration. The study participant's contact information will be securely stored at each clinical site for internal use during the study. At the end of the study, all records will continue to be kept in a secure location for as long a period as dictated by local IRB and institutional regulations.

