Hispanic or Latino	5	+	6	= 11
Not Hispanic or Latino	22	+	22	= 44
Ethnic Category: Total of all subjects	27	+	28	= 55
Racial Category				
American Indian or Alaskan Native	0	+	0	= 0
Asian	3	+	3	= 6
Black or African American	6	+	7	= 13
Native Hawaiian or other Pacific Islander	0	+	0	= 0
White	18	+	18	= 36
Racial Category: Total of all subjects	27	+	28	= 55

13.4 Analysis of the Adverse Event Data:

All patients who receive at least 1 dose of protocol therapy will be included in the safety analyses. Adverse event data will be summarized in stratum specific tables which will incorporate dose, attribution as well as grade information.

13.5 Data analysis plan for the secondary objectives:

Any objective responses (PR+CR) which may be observed in this trial will be described by dose and by histology. We will also report prolonged disease stabilizations in a descriptive fashion.

The biology and PD/PG studies are optional in this trial and thus data will be available only from a subset of patients who are likely to represent a variety of histologies. The data generated as part of these correlative studies will be described and summarized in an exploratory fashion via summary statistics and frequency tables as appropriate.

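### The toxicity tables in 13.4 make no reference to pre-therapy grade, so laboratory abnormalities present at entry can be tabulated as on-study toxicity

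*Combined protocol and SAP*

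**What the plan says.** **Recording.** On baseline, Section 7 says: "Any baseline (pretreatment) abnormalities observed during the initial physical examination should be recorded in the Rave database". It does not mention laboratory results. For treatment and the 30 days after it: "Only record Grades 1 and 2 adverse events if the attribution is at least possibly related to PD-0332991". Grade 3-4 events and deaths are recorded whatever their attribution. On the five-level scale in 7.2, Possible requires only that the drug may be the cause.

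**Tabulation.** Section 13.4 includes every patient who took at least one dose and states: "Adverse event data will be summarized in stratum specific tables which will incorporate dose, attribution as well as grade information". It has no rule on pre-therapy grade, worsening or treatment emergence.

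**Laboratory data.** The study calendar (Section 10) marks "CBC - WBC, HgB, Hct, Platelets, ANC, ALC", chemistry and liver tests at pre-therapy, and its footnote A asks for "CBC with differential at baseline and q weekly during each cycle for the first 3 cycles". Section 5.5.1 says: "Pre-treatment, on-study and off-treatment data, as well as patient response data are to be recorded in the electronic data collection screens". Section 12.3 adds: "Sites must upload all source documentation which supports the eligibility of the participant to the PBTC via the RAVE database".

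**Entry limits.** Section 3.2.10 sets limits for ANC (1,000/mm³), platelets (100,000/mm³), hemoglobin (8 g/dL), bilirubin (1.5 x ULN), AST/ALT (3 x ULN), albumin and renal function, the same in both strata. It sets none for lymphocytes, total white cells or electrolytes.

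**Baseline used elsewhere.** Section 2.4.2 expresses the pharmacodynamic measure as "percentage change in ANC and platelets compared to baseline". Section 5.5.3 follows toxicities until they resolve or return to baseline.

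**The concern.** Describing toxicity is part of primary objective 1.1.1. The trial is stratified because heavier pretreatment is expected to bring more hematologic toxicity. There is no control arm, so the patient's own entry value is the only reference for a laboratory event. If the tables ignore it, a count that was low at entry and stayed low looks the same as a count that the drug lowered.

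Stratum II is defined by more than four prior regimens, craniospinal irradiation or myeloablative therapy, so its patients plausibly enter with lower counts. Its tables could then show more cytopenia than Stratum I even if the drug acted equally in both.

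**Working it through.** **Step 1. Follow an unchanged entry abnormality through the rules.**

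- *Grade 3-4 at entry, no entry limit (lymphocytes, electrolytes, possibly total white cells).* It is not a physical-examination finding, so the Section 7 baseline sentence does not cover it. On treatment it meets the Grade 3-4 rule whatever its attribution. It can enter the 13.4 tables with its grade and attribution and no entry grade beside it. Section 7.3.3 confirms that lymphopenia up to Grade 4, with any attribution, still goes through routine reporting. Total white cells have no limit of their own, although the ANC floor implies at least 1,000/mm³.
- *Grade 1-2 at entry, within the limits (for example hemoglobin above 8 g/dL but below normal, or AST/ALT up to 3 x ULN).* It is recorded only if judged at least possibly related. If judged unlikely or unrelated, it never reaches the tables.

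**Step 2. Does attribution filter out the second group?** Only in part. Possible is a low bar, and the risk list in 7.1 names anemia, neutrophil decrease and white cell decrease as likely drug effects (over 20%), and platelet, lymphocyte, AST and ALT changes as less likely ones. These are the terms at issue, and no instruction tells the investigator to compare with the entry value.

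**Step 3. Size per patient.** The plan gives no figure for entry abnormalities, so there is none to reproduce. The Stratum II denominator does reproduce: 2 dose levels x 6 + 6 in expansion = 18, as stated in 13.3. One unchanged patient adds 1/18 = 5.6 points there, and 1/21 = 4.8 points among the 21 enrolled in Stratum I.

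**Step 4. Illustration; every rate is assumed.** Let b be the share with a given abnormality at entry, q the new incidence among the others, and f the share of entry abnormalities tabulated as drug-related. Suppose entry abnormalities do not worsen.

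Tabulated incidence = b x f + (1 - b) x q; truly new = (1 - b) x q.

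With b = 0.3, q = 0.2, n = 18:

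| f | Tabulated | Patients of 18 | Truly new |
|---|---|---|---|
| 0 | 0 + 0.14 = 14% | 2.5 | 14% |
| 0.5 | 0.15 + 0.14 = 29% | 5.2 | 14% |
| 1 | 0.30 + 0.14 = 44% | 7.9 | 14% |

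With q = 0.2 and f = 1, moving b from 0.1 to 0.5 gives 28% to 60% tabulated, against 18% to 10% truly new. The result depends on b and f, and the documents give neither.

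**Step 5. Gap between strata with no new events.** Gap = f x (b in Stratum II - b in Stratum I). Assume 10-40% in Stratum II and 5-15% in Stratum I. At f = 1 the gap runs from 10 - 15 = -5 to 40 - 5 = +35 points, with 25 - 10 = 15 at the midpoints. At f = 0.5 it runs from -2.5 to +17.5.

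**Step 6. Is there a route to dose finding?** Under 5.2, a listed event is a DLT only if at least possibly related and within the dose-finding period. Section 5.2.1.2 excludes lymphopenia from Grade 4 hematologic DLT. Section 13.2 allows de-escalation to be considered on the number of toxicities in the expansion cohort and does not expressly limit these to DLTs, but nothing there says that entry abnormalities would be counted.

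**The case against.** The strongest reply is that attribution already does this work. A stable Grade 2 anemia judged unrelated is never recorded. A Grade 3-4 event is recorded, but 13.4 shows its attribution beside its grade. An investigator who holds an unchanged pre-therapy count has good reason to call the event unrelated. The entry limits are identical in both strata, and 3.2.5 requires recovery from acute toxicity of earlier therapy. No between-stratum test is planned: each stratum is analyzed independently and descriptively. Tabulating by attribution and tabulating by worsening are both recognized conventions.

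Much of this stands. A reader might infer from the Section 7 sentence that baseline laboratory values are not captured at all. The documents do not support that: the calendar, 5.5.1 and 12.3 all bring them in. A reader might also infer that every entry abnormality counts as drug toxicity. That does not follow either, because the attribution rules remove or label some of them.

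What does not stand is that attribution closes the gap. It is a judgment made event by event, with a low threshold and no instruction to use the entry value. It does not keep unrelated Grade 3-4 abnormalities out of the record. Equal limits do not imply equal distributions within them, and lymphocytes and electrolytes have no limit.

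**Conclusion.** The gap is real but narrow. The Section 7 baseline sentence leaves out laboratory findings, and 13.4 does not use the pre-therapy values that the trial collects. Entry abnormalities can therefore be tabulated as on-study toxicity and can inflate the descriptive rates that serve objective 1.1.1. A larger effect in Stratum II is plausible from how that stratum is defined, but no data on it are given.

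The firm figure is 5.6 points per affected patient, if Stratum II reaches 18. A reader might take the 35-point end of Step 5 as the likely distortion. It pairs the highest assumed Stratum II rate with the lowest assumed Stratum I rate and counts every entry abnormality as drug-related, and the documents support none of these inputs. CTCAE cut-offs are not printed in the protocol, so the grade that each entry limit admits is also an assumption.

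A reader might also infer that the MTD is at risk. Step 6 shows no such effect. The point concerns how toxicity is described, not how the dose was chosen.

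**What to change.** 1. In Section 7, extend the baseline sentence to all pre-therapy laboratory evaluations in the study calendar, graded by CTCAE v4.0.
2. In 13.4, keep the planned tables by attribution. For laboratory events, add the count of patients whose grade worsened from the pre-therapy grade.
3. Add shift tables of pre-therapy grade by worst on-treatment grade, once for course 1 and once for all courses, by stratum and dose level. Cover ANC, platelets, hemoglobin, total white cells, lymphocytes, AST/ALT, bilirubin and electrolytes.

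DLT definitions and the Rolling-6 rule stay unchanged.

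The cost is a short wording change and a few extra tables from values already collected. Only 4 Stratum II patients were enrolled as of version 8.0, so most of that stratum can be handled prospectively; Stratum I can use its stored pre-therapy values. One drawback is that a worsening-only count omits an abnormality that resolves and then recurs at its entry grade. That is why the full tables are kept beside it.

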7.1 Comprehensive Adverse Events and Potential Risks list (CAEPR)

Comprehensive Adverse Events and Potential Risks list (CAEPR) for Palbociclib (PD-0332991, NSC 772256)

The Comprehensive Adverse Events and Potential Risks list (CAEPR) provides a single list of reported and/or potential adverse events (AE) associated with an agent using a uniform presentation of events by body system. Refer to the 'CTEP, NCI Guidelines: Adverse Event Reporting Requirements' http://ctep.cancer.gov/protocolDevelopment/electronic_applications/docs/aeguidelines.pdf for further clarification. Frequency is provided based on 1751 patients. Below is the CAEPR for Palbociclib (PD-0332991).

Version 2.3, January 25, 2018¹

Adverse Events with Possible Relationship to Palbociclib (PD-0332991) (CTCAE 5.0 Term) [n= 1751]		
Likely (>20%)	Less Likely (<=20%)	Rare but Serious (<3%)
BLOOD AND LYMPHATIC SYSTEM DISORDERS		
Anemia		
		Febrile neutropenia
EYE DISORDERS		
	Blurred vision	
	Dry eye	
	Watering eyes	
GASTROINTESTINAL DISORDERS		
	Constipation	
	Diarrhea	
	Mucositis oral	
Nausea		
	Vomiting	
GENERAL DISORDERS AND ADMINISTRATION SITE CONDITIONS		
Fatigue		
	Fever	
INFECTIONS AND INFESTATIONS		
Infection ²		
INVESTIGATIONS		
	Alanine aminotransferase increased	
	Aspartate aminotransferase increased	
	Lymphocyte count decreased	
Neutrophil count decreased		
	Platelet count decreased	
White blood cell decreased		
METABOLISM AND NUTRITION DISORDERS		
	Anorexia	
NERVOUS SYSTEM DISORDERS		
	Dysgeusia	
	Headache ³	
RESPIRATORY, THORACIC AND MEDIASTINAL DISORDERS		

Adverse Events with Possible Relationship to Palbociclib (PD-0332991) (CTCAE 5.0 Term) [n= 1751]		
Likely (>20%)	Less Likely (<=20%)	Rare but Serious (<3%)
	Epistaxis	
SKIN AND SUBCUTANEOUS TISSUE DISORDERS		
	Alopecia	
	Dry skin	
	Skin and subcutaneous tissue disorders - Other (rash) ⁴	

¹This table will be updated as the toxicity profile of the agent is revised. Updates will be distributed to all Principal Investigators at the time of revision. The current version can be obtained by contacting [contact]. Your name, the name of the investigator, the protocol and the agent should be included in the e-mail.

²Infection includes all 75 infection sites under the INFECTIONS AND INFESTATIONS SOC.

³Headache has been observed in trials using Palbociclib (PD-0332991) in combination with fulvestrant.

⁴Rash includes rash, rash maculo-papular, erythema, erythematous rash, erysipelas, rash pruritic, rash papular, generalized rash, exanthema, allergic dermatitis, dermatitis acneiform, and dermatitis.

⁵Peripheral neuropathy includes both peripheral motor neuropathy and peripheral sensory neuropathy under the NERVOUS SYSTEM DISORDERS SOC.

Adverse events reported on palbociclib (PD-0332991) trials, but for which there is insufficient evidence to suggest that there was a reasonable possibility that palbociclib (PD-0332991) caused the adverse event:

BLOOD AND LYMPHATIC SYSTEM DISORDERS - Bone marrow hypocellular; Blood and lymphatic system disorders - Other (pancytopenia)

CARDIAC DISORDERS - Atrial fibrillation; Cardiac arrest; Cardiac disorders - Other (paroxysmal atrial fibrillation with rapid ventricular response); Palpitations; Pericarditis; Sinus bradycardia; Supraventricular tachycardia

EYE DISORDERS - Cataract; Eye disorders - Other (retinal hemorrhage)

GASTROINTESTINAL DISORDERS - Abdominal distension; Abdominal pain; Ascites; Colitis; Colonic perforation; Dry mouth; Dyspepsia; Dysphagia; Esophageal stenosis; Flatulence; Gastric hemorrhage; Gastrointestinal disorders - Other (gastrointestinal hemorrhage); Intra-abdominal hemorrhage; Lower gastrointestinal hemorrhage; Small intestinal obstruction; Small intestinal perforation; Upper gastrointestinal hemorrhage

GENERAL DISORDERS AND ADMINISTRATION SITE CONDITIONS - Chills; Death NOS; Edema limbs; Localized edema; Malaise; Non-cardiac chest pain; Pain; Sudden death NOS

HEPATOBIILIARY DISORDERS - Hepatic failure; Hepatobiliary disorders - Other (bile duct obstruction); Hepatobiliary disorders - Other (jaundice)

IMMUNE SYSTEM DISORDERS - Allergic reaction

INJURY, POISONING AND PROCEDURAL COMPLICATIONS - Fall; Fracture

INVESTIGATIONS - Alkaline phosphatase increased; Blood bilirubin increased; CPK increased; Creatinine increased; Ejection fraction decreased; GGT increased; INR increased; Weight loss

METABOLISM AND NUTRITION DISORDERS - Dehydration; Hypercalcemia; Hyperglycemia; Hyperkalemia; Hypermagnesemia; Hyperuricemia; Hypoalbuminemia; Hypocalcemia; Hypokalemia; Hyponatremia; Hypophosphatemia; Metabolism and nutrition disorders - Other (failure to thrive)

MUSCULOSKELETAL AND CONNECTIVE TISSUE DISORDERS - Arthralgia; Back pain; Flank pain;

Generalized muscle weakness; Muscle cramp; Musculoskeletal and connective tissue disorder - Other (osteomyelitis); Myalgia; Neck pain; Osteonecrosis; Pain in extremity
NEOPLASMS BENIGN, MALIGNANT AND UNSPECIFIED (INCL. CYSTS AND POLYPS) - Treatment related secondary malignancy
NERVOUS SYSTEM DISORDERS - Dizziness; Dysesthesia; Dysphasia; Intracranial hemorrhage; Nervous system disorders - Other (peripheral neuropathy)⁵; Syncope
PSYCHIATRIC DISORDERS - Confusion; Insomnia; Psychiatric disorders - Other (altered mental status)
RENAL AND URINARY DISORDERS - Acute kidney injury; Hematuria
RESPIRATORY, THORACIC AND MEDIASTINAL DISORDERS - Cough; Dyspnea; Hypoxia; Oropharyngeal pain; Pleural effusion; Pneumonitis; Postnasal drip; Pulmonary edema; Pulmonary hypertension
SKIN AND SUBCUTANEOUS TISSUE DISORDERS - Hyperhidrosis; Pruritus
VASCULAR DISORDERS - Hypertension; Hypotension

Note: Palbociclib (PD-0332991) in combination with other agents could cause an exacerbation of any adverse event currently known to be caused by the other agent, or the combination may result in events never previously associated with either agent.

